## **7.2 Sample Size and Accrual**

We know of no detailed published data for the primary and secondary endpoints for the study specific p16+/HPV+ OP-SCCA patient population of interest. However, the ‘historical’ data from sixty patients (updated since publication) treated at UVA provides us with a reliable source to guide sample size determination and monitoring guidelines. For those sixty patients, N0 recurrence occurred in 1/60=1.7% and locoregional failure occurred in 6/60=10% with the upper limit of a one-sided 95% CI being 7.7% and 19%, respectively. Three-year PFS from start of radiation treatment is 80% (95% CI (67, 88%)). For sample determination, these estimates will be used to define the null and alternative 3-

year PFS rates. Specifically, we would like to be able to differentiate between a null 3-year PFS rate of 80% versus the alternative of 67%. Assuming uniform accrual of 15 eligible patients a year for 3 years, a minimum follow-up time of 3 years, PFS is exponentially distributed, a one-sided 10% level test then accrual of 45 eligible patients provides approximately 89% power at the alternative. If the exponential assumption is not supported by the data then accrual of 45 eligible patients results in 80% power to test for a decrease of 14% in 3-year PFS with a one-sided 10% exact binomial level test.

A sequential probability ratio test (SPRT) based upon a binomial test of proportions for N0 control rates will be used. Only the upper boundary will be used for monitoring to protect against excessive failures. The stopping boundary are for a SPRT contrasting a 2% versus 8% N0 control rate, with nominal type I and II errors of 10% and 10%, respectively. The slope of the parallel lines for monitoring is 0.043 and the intercepts are 1.516 and 1.516.

Stopping guideline for N0 Failure	
Number of participants	Boundary
2-9	$\geq 2$
10-33	$\geq 3$
34-45	$\geq 4$

For estimation of locoregional control, a sample size of 45 eligible patients produces a two-sided 90% confidence interval with a width equal to 0.17 when the sample proportion is assumed at the observed historical rate of 10%.

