UVA treats approximately 20-25 oropharyngeal cancer patients annually with definitive radiation or chemoradiation. We anticipate an accrual rate of 15-20 cases per year over 3 years (n=45). We will recruit a total of 45 patients with Stage I-IVb, p16-positive OPSCC who are candidates for radiotherapy. All patients will receive IMRT as part of their cancer treatment and will be followed on this study for 3 years after treatment.

The purpose of this study is to test the overall hypothesis that reduced intensity radiation treatment (39.6 Gy) to the N0 nodes in OPSCC patients with p16 positive tumors can reduce toxicity without compromising treatment efficacy. This represents a 10% reduction from 44 Gy (the minimum dose that the current NCCN guidelines recommend for the elective treatment of N0 nodes of patients with squamous cell carcinoma of the head and neck) and a 20% reduction from our institutional standard of care of 50.4 Gy. Efficacy endpoints will include N0 nodal control, disease-free survival, and overall survival. Safety will be assessed by grading of acute and late radiation-induced toxicity including acute radiation dermatitis and late subcutaneous fibrosis, neck dissection complication rate, xerostomia and dysphagia.

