#### 4.7 Duration of Follow Up

Patients will be followed for three years after completion of the treatment or withdrawal from the study, or until death (whichever occurs first). All patients, regardless of the duration of therapy, will be asked to complete QOL questionnaires every 3 months for the first year (starting at 6 months post-IMRT), and every 6 months for the second and third years.

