#### **4.9 Removal of Patients from Protocol Therapy**

Patients enrolled in this study will receive 7 weeks of IMRT and then be followed for up to 3 years. Patients may discontinue from the study at any time and for any of the following reasons:

- Disease progression
- Inter-current illness that prevents further administration of treatment
- Unacceptable adverse event(s)
- Patient decides to withdraw from the study
- General or specific changes in the patient's condition render the patient unacceptable for further treatment in the judgment of the investigator
- Death

The reason for study removal and the date the patient is removed will be documented in the Case Report Form. Patients discontinued or withdrawn from protocol therapy will continue to be treated per standard of care.

If a patient discontinues or is withdrawn from the study for the above listed reasons, then all data collected prior to discontinuation/ withdrawal will be included in the final analysis.

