**Table 2: Follow-Up Assessments**

	Months  following last IMRT									
	3	6	9	12	15	18	21	24	30	36
Contrast enhanced CT (or MR) or PET CT	X 			X				X		X
QOL questionnaires 	X	X	X	X	X	X	X	X	X	X
History	X	X	X	X	X	X	X	X	X	X
Physical Exam 	X	X	X	X	X	X	X	X	X	X
Vital Signs (BP, HR, temp)	X	X	X	X	X	X	X	X	X	X
Zubrod Performance Status	X	X	X	X	X	X	X	X	X	X
Toxicity Assessments 	X	X	X	X	X	X	X	X	X	X
Disease status 	X	X	X	X	X	X	X	X	X	X

 Must be performed within 28 days of initiation of study treatment, unless a different timeframe is specified

 Assessments should be conducted between 4-6 weeks following the last IMRT treatment

 Includes height and body surface area (BSA); height is collected at pre-study visit only

 p16 expression for eligibility must be detected by immunohistochemistry and in situ hybridization (HPV)

 Must be performed within 8 weeks of start of treatment for cancer

 WOCBP must have a negative serum pregnancy test at least 14 days prior to initiation of cancer treatment

 Acute AEs will be collected up to 90 days following the last IMRT; late radiation toxicities will be collected from 3 months up to 3 years following the last IMRT

 Disease status should be assessed at each follow-up, using RECIST criteria

 Assessments should be performed  $\pm$  2 weeks from date

The imaging assessments at 3 months post-IMRT are optional.

 May be completed by mail if patient is not scheduled for or misses a clinic visit

 Follow-up physical exams may include a flexible fiberoptic nasolaryngoscopy

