## 5.4 Post-Treatment/Follow-up Assessments

The below follow-up evaluations should be performed at the intervals specified in Table 2 following the last IMRT:

- Contrast enhanced CT (or MR) or PET CT should be performed every 12 months to assess for disease progression
- The following should be performed each time a patient is seen in clinic, per standard care (approximately every 3 months for 2 years, every 6 months in year 3). If a clinic visit is missed, then these assessments should be performed at the next visit:
  - History and Physical (including performance status)
  - Vital signs
  - Performance Status
  - Disease status
  - Acute and late toxicity assessments
- QOL questionnaires should be performed at clinic visits. If no clinic visit is scheduled it can be completed by mail and reviewed with the patient at the next clinic visit.
- Acute toxicity assessments should be performed to collect signs of radiation toxicity which occur up to 90 days following the last IMRT with grading per version 4 CTCAE.
- Late radiation toxicity (effects that occur after 90 days following completion of IMRT) will be evaluated at the time points shown in Table 2: Follow-up Assessments (every 3 months until 24 months after completion of IMRT and then every 6 months from 24-36 months after completion of IMRT). Late Toxicity will be scored per version 4 CTCAE.

In addition, if a patient has an unresolved adverse event at the end of study treatment, the event should be followed every 4-6 weeks until it has resolved, returned to baseline or is deemed irreversible, whichever is longer.

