### **6.2.2 Progression-Free Survival**

Progression-Free Survival (PFS) is defined as the duration of time from start of treatment to time of recurrence/progression or death from any cause, whichever occurs first. Progression will be measured as defined by the RECIST criteria (Section 6.1). Patients who do not experience an event (recurrence/progression or death) will be censored at date of last contact.

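### The 89% power for 3-year PFS assumes 3 to 6 years of follow-up per patient; the follow-up sections plan 3 years, which gives about 77–85%

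*Combined protocol and SAP*

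**What the plan says.** Section 7.2 sets a null 3-year PFS of 80% against an alternative of 67%, tested one-sided at 10% under exponential PFS. The stated design is "Assuming uniform accrual of 15 eligible patients a year for 3 years, a minimum follow-up time of 3 years", and the result is that "accrual of 45 eligible patients provides approximately 89% power at the alternative". Section 7.3 gives the two hazards, 0.0744 and 0.1335 per year, but no test statistic. Section 7.1 also treats 3 years as a minimum when it defines the control rates.

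The operational sections describe a fixed period:

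- 1.1: patients "will be followed on this study for 3 years after treatment".
- 4.7: "Patients will be followed for three years after completion of the treatment", or until death.
- 4.9: patients "will receive 7 weeks of IMRT and then be followed for up to 3 years".
- 5.4: clinic assessments run "approximately every 3 months for 2 years, every 6 months in year 3".
- Table 2: the last column is month 36. Its footnote on disease status reads "Disease status should be assessed at each follow-up, using RECIST criteria", so the last scheduled assessment is at that visit.

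Section 6.2.2 defines PFS as the "duration of time from start of treatment to time of recurrence/progression or death from any cause". Patients without an event are censored when last contacted.

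**The concern.** Three years of accrual plus a minimum of 3 years means that the first patients are observed for up to 6 years and the last for 3. The exponential test gains its power from events over all of that time. If every patient leaves follow-up 3 years after treatment, the extra 0 to 3 years per patient do not exist and the events expected in them are not counted.

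This is a dose-reduction trial, so the power of this test is the chance of detecting harm. PFS is a secondary endpoint and 7.3 attaches no go/no-go rule to the hazard test. But 7.2 uses the calculation to support n=45, and 7.1 lists 3-year disease-free survival among the conditions for taking the regimen further.

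**Working it through.** **Inputs**

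- 3-year PFS 80% and 67%; n = 45; 15 patients a year for 3 years; one-sided 10% (7.2).
- Hazards: λ0 = −ln(0.80)/3 = 0.0744 and λ1 = −ln(0.67)/3 = 0.1335, matching 7.3. Ratio λ1/λ0 = 1.79.
- Follow-up (a): 3 to 6 years, as in 7.2.
- Follow-up (b): 3 years after a 7-week course, counted from treatment start: 3 + 7/52 = 3.13 years (4.6, 4.7, 6.2.2).
- Follow-up (c): 3.0 years from treatment start, as a lower case.
- Dropout: none stated, taken as zero (assumption).

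**Expected events**

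(a) Uniform accrual over 3 years plus 3 years: P(event) = 1 − (e^(−3λ) − e^(−6λ))/(3λ).

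- Null: 1 − (0.80 − 0.64)/0.2231 = 0.283; × 45 = 12.7.
- Alternative: 1 − (0.67 − 0.4489)/0.4005 = 0.448; × 45 = 20.2.

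(b) and (c) Fixed follow-up F: P(event) = 1 − e^(−λF).

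- F = 3.13: 9.4 events under the null, 15.4 under the alternative.
- F = 3.0: 45 × 0.20 = 9.0 and 45 × 0.33 = 14.9.

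**Power**

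Since 7.3 names no test, several were tried. With d the expected events under the alternative, two have closed forms:

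- Hazard-scale normal: Φ{[((λ1 − λ0)/λ0)·√d − 1.2816]/(λ1/λ0)}. At (a): (0.795 × 4.490 − 1.2816)/1.795 = 1.274, so 89.9%. At (b): (0.795 × 3.923 − 1.2816)/1.795 = 1.023, so 84.7%.
- Log-rate normal: Φ{ln(λ1/λ0)·√d − 1.2816}. At (a): 0.585 × 4.490 − 1.2816 = 1.344, so 91.1%. At (b): 0.585 × 3.923 − 1.2816 = 1.013, so 84.4%.

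The others were simulated with 400,000 trials of 45 patients. The chi-square rule rejects when 2·λ0·T is below the 10th percentile of chi-square on 2d+2 degrees of freedom, where T is total observed time and d here is the observed number of events. The size-held test rejects when d/T exceeds its 90th percentile under the null.

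| Test | (a) 3–6 y | (b) 3.13 y | (c) 3.0 y | Actual size (a / b / c) |
|---|---|---|---|---|
| Hazard-scale normal | 89.9% | 84.7% | 84.0% | approximation |
| Log-rate normal | 91.1% | 84.4% | 83.5% | approximation |
| Chi-square (2d+2) | 89.1% | 82.0% | 81.9% | 13.0 / 12.9 / 13.7% |
| Score | 87.1% | 80.2% | 77.6% | 10.9 / 11.5 / 10.4% |
| Size held at 10% | 86.1% | 78.0% | 76.9% | 10.0% |
| Likelihood ratio | 85.7% | 77.4% | 76.6% | 9.7 / 9.7 / 9.8% |

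The plan's 89% is reproduced at (a): chi-square (2d+2) and hazard-scale normal both fall within about 1 point of it. Those same two give 82–85% at (b). The loss within a test is 5.2 to 8.3 points at (b) and 5.9 to 9.5 points at (c).

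A chi-square rule on 2d degrees of freedom gives 83.8%, 73.6% and 74.1%. It is left out of the range because it is 5 points below 89% even under 7.2's own assumptions.

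**Fallback**

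The exact binomial test with n = 45 rejects at 32 or fewer progression-free patients. Its size is 9.95% and its power at 66% (a 14-point fall) is 81.0%, so the printed 80% is correct. It needs only 3 years of observation and is unaffected. At 67% its power is 76.9%.

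**The case against.** Section 7.2 states its follow-up assumption openly, and 89% is about right under it. Section 7.1 also speaks of a minimum, and 6.2.2 censors at last contact rather than at month 36. Section 5.4 ties disease-status checks to standard-care visits in a single-institution trial, so later routine contact could supply PFS data without a protocol visit. On this reading 7.2 contains no slip. This stands as far as intent goes: the documents do not say which follow-up was meant. It does not remove the conflict, because 4.9 states a maximum and no section schedules contact after month 36.

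Some planning formulas do give about 89% on roughly 3 years. A cube-root form that applies the null standard deviation at the alternative gives 89.5% at 3.13 years and 88.6% at 3.0 years. So the printed figure does not by itself prove that 3 to 6 years was used. But no true 10%-level test attains those values: the most powerful one reaches about 78% at 3.13 years and 77% at 3.0 years.

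Setting the full 77–85% range against 89% also mixes choice of test with length of follow-up. That is fair: the size-held and likelihood-ratio tests already sit at about 86% on 3 to 6 years. The like-for-like effect of follow-up is the loss within a test.

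Finally, the primary endpoint is N0 nodal control, with its own sequential monitoring rule, and both the binomial fallback and the locoregional interval width are computed separately. That limits the weight of the point.

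**Conclusion.** The concern holds. The follow-up as scheduled does not deliver the stated 89%. If follow-up ends 3 years after treatment, power is about 77–85% depending on the test: 82–85% for the two tests closest to 89% under 7.2's assumptions, and about 78% at a true one-sided 10% size.

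The type II error is then about 15–23%, against the 11% that 7.2 implies; a fall from 80% to 67% would be missed about one time in four to seven rather than one in nine. Part of that contrast is choice of test. Like for like, the miss rate rises from 10.1% to 15.3% (hazard-scale normal) or from 14.3% to 22.6% (likelihood ratio).

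These figures rest on exponential PFS, no dropout, and no PFS data beyond 3 years after treatment. If observation until the last patient reaches 3 years was intended, 89% can stand subject to the test named; at a true 10% size it is 86%. The point should be fixed, but it does not touch the primary endpoint.

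**What to change.** 1. In 7.3, name the exponential test and state the follow-up it uses.
2. In 7.2, recompute and restate the power with that test on that follow-up.
3. Make 1.1, 4.7, 4.9, 5.4, Table 2 and 7.2 agree. If follow-up ends 3 years after treatment, remove the 3-to-6-year assumption from the power statement. If longer PFS follow-up was intended, the follow-up sections must say so and state how disease status is obtained after month 36.

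If the 3-year plan stands, the cost is wording only, with no added patients or visits, and the price is a less favourable stated power. If longer follow-up was intended, the cost is the added follow-up that 7.2 already assumes.

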## **6.2 Other Measures of Effect**

### **6.2.1 N0 nodal control**

The N0 nodal volumes will be defined prior to initiation of the radiation treatment regimen by PET scan and contrast enhanced CT and MR scans performed as part of the pre-study assessments. N0 control will be assessed by weekly physical exams performed during treatment and CT scan of the neck performed at 4- 6 weeks and annually post-treatment. Patients with observed involvement of any of the N0 nodes at any post-treatment interval will be considered to have an N0 failure.

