### **7.1 Study Design/Endpoints**

Estimation and safety monitoring for N0 nodal control, locoregional control and 3-year progression-free survival guided sample size determination and monitoring

rules. Data from sixty p16+ OP-SCCA patients treated with standard IMRT at UVA from 2002-2011 with adequate follow-up were used to define ‘historical’ outcomes. The primary endpoint is N0 nodal control rate. In order to consider the treatment regimen worthy of further study the data need to support a N0 control rate no worse than that observed from the historical data. Similar conditions need to be observed for the secondary endpoints of locoregional control rate and 3-year disease-free survival.

N0 nodal control rate is defined as the percent of eligible patients who experience N0 recurrence within the minimum follow-up period of 3 years. Locoregional control rate is defined as the percent of eligible patients who experience local and/or regional failure within the minimum follow-up period of 3 years. The N0 neck represents lymph node regions of the neck that were not clinically or radiographically determined to be pathologically involved with metastatic disease to regional lymph nodes at initial presentation. N0 recurrence = failure in the N0 neck region. Isolated N0 recurrence = failure in the N0 neck region without failure elsewhere. Local (primary) recurrence = failure at the initial site of disease. Regional (nodal) recurrence = failure in lymph nodes in the neck (includes N0 recurrence). Distant recurrence = metastatic failure. Progression-free survival (PFS) is defined in section 6.2.2.

Safety is determined by frequency and severity of adverse events (AEs) related to treatment, and are classified and graded according to CTCAE version 4. AEs related to swallowing function during and after treatment will be assessed. Other endpoints of interest include locoregional recurrence-free survival, dose to regional organs at risk (OARs compared to if the N0 volumes received 50 Gy), and QOL as measured by subject-reported functional outcome questionnaires that will quantify patient-reported speech and swallowing function [MD Anderson Symptom Inventory – Head & Neck (MDASI-HN), MDADI (MD Anderson Dysphagia Index) and VHI-10 (Voice Handicap Index)].

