### **9.1 UVA Cancer Center Data Safety Monitoring Committee**

The University of Virginia Cancer Center Data and Safety Monitoring Committee (DSMC) will provide oversight of the conduct of this study. The CC DSMC will report to the UVA Protocol Review Committee (PRC).

The DSMC will review the following:

- All adverse events
- Audit results
- Application of study designed stopping/decision rules
- Whether the study accrual pattern warrants continuation/action
- Protocol violations

The CC DSMC will meet every month for aggregate review of AE data. Tracking reports of the meetings are available to the PI for review. Issues of immediate concern by the DSMC are brought to the attention of the PI (and if appropriate to the PRC and IRB) and a formal response from the PI is requested. Per the Cancer Center NIH approved institutional plan this study will be audited approximately every 12 months.

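### The nominal 10%/10% errors given for the N0-failure stopping rule are not those of the upper-boundary-only rule ending at 45 patients, which misses an 8% failure rate about 41% of the time even when checked after every patient

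*Combined protocol and SAP*

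**What the plan says.** Section 7.2 defines an SPRT for N0 outcome, "contrasting a 2% versus 8% N0 control rate", "with nominal type I and II errors of 10% and 10%, respectively". It adds: "Only the upper boundary will be used for monitoring to protect against excessive failures". The line is given as follows: "The slope of the parallel lines for monitoring is 0.043 and the intercepts are 1.516 and 1.516". The stopping table, headed as a guideline for N0 failure, requires at least 2 failures for 2-9 participants, at least 3 for 10-33 and at least 4 for 34-45. No other error rate, power or stopping probability for this rule appears in the document.

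Three other sections bear on how the rule would run:

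- Section 7.1 defines the N0 nodal control rate as "the percent of eligible patients who experience N0 recurrence within the minimum follow-up period of 3 years".
- Section 6.2.1 has N0 control assessed by weekly examination during treatment and "CT scan of the neck performed at 4- 6 weeks and annually post-treatment".
- Section 9.1 lists "Application of study designed stopping/decision rules" among the monitoring committee's review items. It has the committee meet monthly for aggregate adverse-event review, but ties no N0 look schedule to those meetings.

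**The concern.** The rule guards the primary endpoint, and its stated purpose is protection against excess failures. The property that matters most is therefore the chance that it triggers when the N0 failure rate really is high. The only figures offered on this are 10% and 10%, and they belong to a different procedure from the one printed. A committee member who relied on them would expect an 8% failure rate to go undetected in about 1 trial in 10.

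Two slips sit beside this. The table does not follow from the line at every sample size, so the same section gives two different stopping decisions at some values of n. The 2% and 8% are also called control rates when they can only be failure rates.

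**Working it through.** **Inputs (section 7.2).** p0 = 0.02, p1 = 0.08, alpha = beta = 0.10; upper boundary only; at most 45 patients; printed table as above.

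**1. Reproduce the plan's line.** With Wald's formulas:

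- k = ln[p1(1 - p0) / (p0(1 - p1))] = ln[(0.08 × 0.98)/(0.02 × 0.92)] = 1.4495
- intercept = ln[(1 - beta)/alpha]/k = ln(9)/k = 2.1972/1.4495 = 1.516, as printed
- slope = ln[(1 - p0)/(1 - p1)]/k = 0.06318/1.4495 = 0.0436, printed as 0.043

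The 10%/10% are thus the inputs that generate the line. For the two-boundary test with no maximum sample size, exact calculation gives errors of about 6.5% and 10.2%, so the nominal miss rate does roughly describe that design.

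**2. Attained properties of the rule as printed.** I used an exact forward recursion on the binomial path to n = 45. At each look, paths at or above the table's boundary are removed and their probability is added to the probability of stopping. Every row assumes that the N0 outcome of each counted patient is known at the look.

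| Looks | Stop at 2% | Stop at 8% | Miss at 8% |
|---|---|---|---|
| After every patient | 3.9% | 58.7% | 41.3% |
| Monthly, 15 patients a year (1.25 per month) | about 3.7% | about 58.4% | about 41.6% |
| At 15, 30 and 45 | 2.6% | 55.3% | 44.7% |
| Once, at 45 (limiting case) | 1.2% | 49.0% | 51.0% |

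The monthly row takes the accrual rate from section 7.2 and the meeting frequency from section 9.1; applying that frequency to the N0 rule is my assumption. At a 10% failure rate the table stops with probability 75% when checked after every patient, 72% with looks at 15, 30 and 45, and 67% with one look at 45.

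**3. Source of the gap.** The cap at 45 is what matters. With no cap, the upper-only rule would stop with probability near 1 at 8%. Ending at 45 with up to 3 failures leaves a large share of paths below the boundary.

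**4. Table against line.** With 1.516 + 0.043n:

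| n | Line | Failures to cross line | Table requires |
|---|---|---|---|
| 9 | 1.903 | 2 | 2 |
| 10 | 1.946 | 2 | 3 |
| 11 | 1.989 | 2 | 3 |
| 12 | 2.032 | 3 | 3 |
| 33 | 2.935 | 3 | 3 |
| 34 | 2.978 | 3 | 4 |
| 35 | 3.021 | 4 | 4 |

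The two agree at every other n from 2 to 45, and the unrounded slope gives the same integers. Checked after every patient, the line stops with probability 4.4% at 2% and 60.2% at 8% (0.0442 and 0.6015, against 0.0386 and 0.5873 for the table). The differences are 0.6 and 1.4 percentage points. With looks at 15, 30 and 45 there is no difference.

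**5. Labels.** The historical N0 recurrence in section 7.2 is 1/60 = 1.7% with an upper limit of 7.7%, and the table concerns failures. The 2% and 8% are therefore failure rates. The wording follows the 7.1 definition, which calls the percent with recurrence a control rate.

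**The case against.** The strongest defence is the word nominal. The section says in the same paragraph that only the upper boundary is used, and nowhere claims 10%/10% as attained rates. A reader might infer that the plan miscalculated its errors. It did not: the line reproduces from the inputs. What stands is an omission. The rule's own error rates are never given, so the nominal ones are all the reader has.

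A second defence is that monitoring could well be frequent. The table has a boundary for every n from 2 to 45, and the committee meets monthly. A reader might take the 51% miss rate as the headline, but it needs a single look after accrual is complete, which no section suggests. Near-continuous checking is the fairer reading, and it still misses about 41%.

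Third, the type I error is below nominal, the rule is more sensitive at higher failure rates, and the table/line mismatch is small. All three are true. The low type I error does not offset weak sensitivity in a boundary meant to catch excess failures. The mismatch still gives opposite instructions at three sample sizes.

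Finally, section 7.1 says that "the data need to support a N0 control rate no worse than that observed from the historical data", and a reader might infer that an uncrossed boundary is meant to show this. The protocol does not say so. It presents the boundary as protection against failures and, in section 7.3, separately plans point estimates and confidence intervals for N0 control. That inference forms no part of this point.

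**Conclusion.** The point holds as a reporting gap with two internal inconsistencies. The stated 10%/10% are not the properties of the adopted rule. Under the most favourable of the schedules considered for the printed table, it stops with probability 3.9% at a 2% failure rate and misses 8% in about 4 trials in 10. Looks at 15, 30 and 45 give 2.6% and a 44.7% miss rate.

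These figures rest on N0 outcomes being known when patients are counted. The plan does not settle this: the endpoint runs over 3 years, scheduled neck CT after the first scan is annual, and nothing says when a patient enters the table's participant count. The attained rates cannot be fixed until that and the look schedule are stated.

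The disagreement at n = 10, 11 and 34 is certain but worth at most about 1.4 percentage points. The label error starts in 7.1 and carries into 7.2; the table's heading leaves the direction of monitoring clear. The sample size and final analysis are not affected. This should be fixed.

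**What to change.** 1. In 7.2, say that 10%/10% are design inputs for an untruncated two-boundary SPRT. State when the boundary will be checked and when a patient counts as a participant in the table. Report the attained stopping probabilities of the upper-only rule to 45 patients under that schedule. If checks follow every patient with outcome known, the printed table gives 3.9% at a 2% failure rate, 28% at 5%, 59% at 8% and 75% at 10%. With looks at 15, 30 and 45 the figures are 2.6%, 25%, 55% and 72%.
2. Reconcile the table and the line at n = 10, 11 and 34, and recompute these probabilities if the table changes.
3. Relabel 2% and 8% as N0 failure rates in 7.2, and correct the 7.1 definition that calls the percent with recurrence a control rate.

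The cost is wording and a short operating-characteristics table, with no extra patients and no redesign. The downside is that the reported chance of detecting an 8% failure rate will be visibly lower than the nominal figures suggest.

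### The N0 stopping table does not follow from the stated SPRT line: at 10, 11 and 34 patients it continues where the line stops

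*Combined protocol and SAP*

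**What the plan says.** Section 7.2 (Sample Size and Accrual) sets the monitoring method: "A sequential probability ratio test (SPRT) based upon a binomial test of proportions for N0 control rates will be used". It is one-sided in use: "Only the upper boundary will be used for monitoring to protect against excessive failures". The inputs are an "SPRT contrasting a 2% versus 8% N0 control rate", "with nominal type I and II errors of 10% and 10%, respectively". The 2% and 8% can only be failure rates, although the text calls them control rates. The line is then given: "The slope of the parallel lines for monitoring is 0.043 and the intercepts are 1.516 and 1.516".

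Directly below is a table headed "Stopping guideline for N0 Failure":

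| Participants | Stop at |
|---|---|
| 2-9 | 2 or more failures |
| 10-33 | 3 or more failures |
| 34-45 | 4 or more failures |

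No rounding rule or adjustment links the line to the table. Section 9.1 lists "Application of study designed stopping/decision rules" among the items that the Data Safety Monitoring Committee (DSMC) reviews.

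**The concern.** A Wald boundary is mechanical: at each n, stopping requires the smallest whole number of failures on or above the line. The line and the table should therefore be one rule written in two ways, and here they are not. The section does not say which governs.

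This is the plan's only numerical stopping boundary, and it guards the primary endpoint in a trial that lowers the dose to the very region being monitored. With 2 failures among 10 patients (20%), 2 among 11 (18%) or 3 among 34 (8.8%), the DSMC would find opposite answers in the same section. The table, which is the easier of the two to apply, gives the less protective answer each time.

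**Working it through.** **Inputs (all from section 7.2).** p0 = 0.02, p1 = 0.08, alpha = 0.10, beta = 0.10, maximum n = 45, stated slope 0.043, stated intercept 1.516.

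**Step 1: reproduce the line.**

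- D = ln[p1(1 - p0) / (p0(1 - p1))] = ln[(0.08 × 0.98) / (0.02 × 0.92)] = 1.4495
- Upper intercept = ln[(1 - beta)/alpha] / D = ln 9 / 1.4495 = 1.516, as stated
- Slope = ln[(1 - p0)/(1 - p1)] / D = ln(0.98/0.92) / 1.4495 = 0.04359; the stated 0.043 is this value truncated

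So the line is the SPRT that the text describes.

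**Step 2: turn the line into cut-points.**

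| n | 1.516 + 0.043n | Exact line (slope 0.04359) | Failures needed, either line | Printed table |
|---|---|---|---|---|
| 9 | 1.903 | 1.908 | 2 | 2 |
| 10 | 1.946 | 1.952 | 2 | **3** |
| 11 | 1.989 | 1.995 | 2 | **3** |
| 12 | 2.032 | 2.039 | 3 | 3 |
| 33 | 2.935 | 2.954 | 3 | 3 |
| 34 | 2.978 | 2.998 | 3 | **4** |
| 35 | 3.021 | 3.041 | 4 | 4 |

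Both slopes give 2 or more for n = 2-11, 3 or more for 12-34 and 4 or more for 35-45.

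**Step 3: confirm without any rounded line.** For x failures in n patients the log-likelihood ratio is x·ln(0.08/0.02) + (n - x)·ln(0.92/0.98). The rule stops when this reaches ln 9 = 2.197.

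- Crosses: 2/10 gives 2.267; 2/11 gives 2.204; 3/34 gives 2.200
- Does not cross: 2/12 gives 2.141; 3/35 gives 2.137

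**Step 4: can a different slope rescue the table?** With intercept 1.516, needing 3 failures at n = 10 requires a slope above (2 - 1.516)/10 = 0.0484. Stopping on 3 at n = 33 requires a slope of at most (3 - 1.516)/33 = 0.0450. No slope meets both conditions.

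**Step 5: size.** Exact recursion to n = 45, with a look after each patient and each outcome known before the next patient is counted:

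| True failure rate | P(stop), table | P(stop), line | Expected n, table | Expected n, line |
|---|---|---|---|---|
| 2% | 3.9% | 4.4% | 44.1 | 43.9 |
| 8% | 58.7% | 60.2% | 31.1 | 30.3 |
| 15% | 94.4% | 94.7% | 17.4 | 16.7 |

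The probability that the second failure falls at n = 10 or 11 is 9p²(1 - p)⁸ + 10p²(1 - p)⁹. This is 0.6% at p = 0.02, 6.0% at 0.08 and 10.7% at 0.15. It measures how often the DSMC would meet the contradiction at that point, not how often a failing regimen escapes stopping, because the table stops most of those trials later.

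**The case against.** The mismatch itself is not in dispute; the case against concerns its weight and which of the two is wrong.

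- **The effect is small.** The net loss in stopping probability is about 1.4 percentage points at 8% and 0.3 at 15%, and the table still stops at 3 failures from n = 10. This stands.
- **The calculation assumes immediate outcomes.** N0 failure is counted over 3 years, with scans at 4-6 weeks and then yearly, and the plan does not say whether the table's participants are enrolled, treated or fully followed. If it counts enrolled patients at 15 a year, n = 10-11 lasts only from month 8.0 (10/15 × 12) to month 9.6 (12/15 × 12), when few outcomes are known. This limits the probabilities in step 5. It does not touch the contradiction between line and table.
- **Two of the three cells are sensitive to rounding.** At a slope of 0.044 the line is 3.012 at n = 34, so that cell then agrees with the table. At n = 11 it is exactly 2.000, so that cell depends on whether reaching the line counts. The table's own sign is at-or-above, and under it n = 11 still disagrees. The n = 10 cell disagrees at 0.043, 0.0436 and 0.044 alike, under either convention.
- **The table might be right and the text wrong.** An SPRT of 2% versus 7.5% with 10%/10% errors has intercept 1.593 and slope 0.0419, and gives exactly 2-9, 10-33 and 34-45. That is a possible origin for the table. But it contradicts both the stated 8% and the stated intercept of 1.516, which agree with each other. It is a reason to offer the sponsor a second route, not a reason to leave the section as it stands.

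**Conclusion.** The concern holds. The stated rates, error levels, intercept and (truncated) slope are mutually consistent; the table is the part that does not follow. Under the stated line and the table's at-or-above sign it is wrong at n = 10, 11 and 34, always in the lenient direction. The n = 10 cell is secure under every slope considered, while the n = 34 cell is narrow (exact line 2.998).

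On average the consequence is slight: at an 8% failure rate, about 1.4 points less chance of stopping and about 0.9 more patients expected, given a look after every patient with outcomes known at once. It still needs correcting, because the section gives two answers at failure counts that the trial could reach and does not say which prevails.

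**What to change.** Replace the table with the cut-points that the stated SPRT gives:

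| Participants | Stop at |
|---|---|
| 2-11 | 2 or more failures |
| 12-34 | 3 or more failures |
| 35-45 | 4 or more failures |

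Give the slope as 0.0436, and say that reaching the line counts as crossing it. If the printed cut-points were intended, keep them and instead state the rates, intercept and slope that produce them. Either way, line and table must describe the same rule.

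The cost is an edit to three table rows and one number. Sample size, endpoints and analyses do not change. Following the line keeps the chance of stopping at a 2% failure rate at 4.4%, well under the nominal 10%.
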